7.3 LOST TO FOLLOW-UP

A student participant will be considered lost to follow-up if he or she fails to complete scheduled assessments and study staff are unable to contact the participant after at least 3 attempts.

The following actions will be taken if a student participant fails to complete a scheduled assessment:

- The site IE will attempt to contact the student participant by telephone and email, reschedule the missed visit as soon as feasible, counsel the student participant on the importance of maintaining the assigned visit schedule and ascertain if the student participant wishes to and/or should continue in the study.
- The IE will ask the counselor if the student participant has changed phone number/email, is attending therapy, and/or has been in contact and may ask the counselor to prompt the student participant to contact study staff.
- Before a student participant is deemed lost to follow-up, the investigator or designee will make every effort to regain contact with the student participant (where possible, 3 telephone calls and, if necessary, a certified letter to the student participant's last known mailing address or local equivalent methods). These contact attempts will be documented in the student participant's medical record or study file.
- Should the student participant continue to be unreachable, he or she will be considered to have withdrawn from the study with a primary reason of lost to follow-up.

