6.1.4 RANDOMIZATION

Following the completion of the baseline assessment, the site PC will review the consent, document the randomization block variables (gender, medication, past suicide attempt), obtain randomization assignment from the Data Center at Duke University, and reveal randomization results to an already assigned counselor. Note that student participants will learn of their treatment assignment by the counselor at their first treatment visit (this procedure was used in the pilot project and received very favorably by students and counselors).

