6.3 MEASURES TO MINIMIZE BIAS: RANDOMIZATION AND BLINDING

Randomization

We will rely on an adaptive-biased coin design¹⁰⁹ to attempt to balance conditions at each stage based on gender, previous suicide attempt(s), and current psychotropic medications. At Stage 2, the PC will obtain information on the blocking variables, along with the tailoring variable, from counselors and the electronic medical record (EMR; Titanium for all sites) prior to randomization. The PC at each site will randomize subjects via the centralized database using a customized system tailored for the SMART design housed at the Duke Data Center.

All assessments of the main endpoints will be performed by the independent evaluators (IEs), who will remain blind to treatment status. It is always possible that student participants could tell the IE during their assessments about the type of therapy they have been receiving. To mitigate this risk, all student participants will be reminded about the importance of not telling the IEs which treatment they received. It is also possible that counselor participants could tell the IE which treatment condition a particular student participant is in; counselor participants will be frequently reminded not to do so. To evaluate how well blinding was maintained, the IEs will be asked to indicate what treatment group(s) they thought the student participant belonged to at the end of stage 1 and, if applicable, at the end of stage 2.

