6.5 CONCOMITANT THERAPY

If it is discovered during or after the study that a participant received a “crossover-treatment” on his/her own or received any other form of therapy, we will document these treatments in the clinical record and on the treatment history form that is completed by the student participant and the IE and develop procedures to minimize this threat as much as possible for use in the large-scale trial.

While clinical and research staff are expected to strongly discourage treatment outside the study, these student participants will continue to be treated within their assigned treatment arm. Stated differently, student participants receiving non-protocol treatments on their own accord are not automatically considered premature terminators. On the other hand, student participant-initiated crossover treatments should prompt consideration of a review of the student participant’s clinical status. An example of this would be the case of a student participant-initiated psychiatric hospitalization for worsening depression, which would automatically lead to premature termination.

Handling of Medications. Student participants will neither be asked to discontinue medications or to start medications as part of the study. Following regular CCC practice, student participants may be referred for a psychiatric consultation if needed. We will stratify on current use of psychotropic medication at both randomization points to equate medication use across

conditions. We will also assess for any mid-treatment use of medications via data collected on the treatment history interview. Approximately a quarter of students presenting to a CCC are already on a psychiatric medication.⁴² This approach to medication reaches a good balance of allowing for medications while not including an active protocol on psychotropic management and it seems appropriate, given the limited evidence of pharmacotherapy-only treatment for SR.¹⁴⁸

7 STUDY INTERVENTION/EXPERIMENTAL MANIPULATION DISCONTINUATION AND PARTICIPANT DISCONTINUATION/WITHDRAWAL

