8.3.3.2 RELATIONSHIP TO STUDY INTERVENTION/EXPERIMENTAL MANIPULATION

All adverse events (AEs) will have their relationship to study procedures, including the intervention, assessed by the student participant's treating counselor and/or IE based on the temporal relationship and his/her clinical judgment. The degree of certainty about causality will be graded using the categories below.

- **Definitely Related** – There is clear evidence to suggest a causal relationship, and other possible contributing factors can be ruled out. The clinical event, including an abnormal laboratory test result, occurs in a plausible time relationship to study procedures administration and cannot be explained by concurrent disease or other drugs or chemicals. The response to withdrawal of the study procedures should be clinically plausible. The event must be pharmacologically or phenomenologically definitive.
- **Possibly Related** – There is some evidence to suggest a causal relationship, and the influence of other factors is unlikely. The clinical event, including an abnormal laboratory test result, occurs within a reasonable time after administration of the study procedures, is unlikely to be attributed to concurrent disease or other drugs or chemicals, and follows a clinically reasonable response on withdrawal.
- **Not related** – A clinical event, including an abnormal laboratory test result, whose temporal relationship to study procedures administration makes a causal relationship improbable (e.g., the event did not occur within a reasonable time after administration of the study procedures) and in which other drugs or chemicals or underlying disease provides plausible explanations (e.g., the participant's clinical condition, other concomitant treatments).

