9.3 CAMPUS TRIAL STATISTICAL ANALYSES

9.3.1 GENERAL APPROACH

Overview and Intent-to-Treat. The proposed trial design of adaptive treatment strategies (ATSSs) is like a factorial design;^{156,157,158,159} different analytic subgroups (see Table 8) are combined to answer different questions. Aim 1 is the trial's primary aim; Aims 2-5 are secondary aims and Aim 6 as an implementation aim. All student participants, once randomized, will be included in the intent-to-treat sample, and every effort will be made to collect all primary and secondary outcomes even if a student participant does not engage in randomly assigned treatments. The primary outcome of interest is suicidal risk, which includes suicidal ideation as well as suicide-related behaviors, such as non-suicidal self-injury (NSSI) and suicide attempts (SAs); however suicidal ideation is the primary DV due to relatively low rates of suicidal behaviors post-baseline with college students. Suicides will be tallied as well. All analyses allow for the inclusion of covariates listed as demographics and covariates in Section 8.1. Covariates will enter the model based in clinical importance (gender, age, current alcohol use, current substance use, etc.) and retained on a case-by-case basis based on statistical significance.

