9.3.2 ANALYSIS OF THE PRIMARY ENDPOINT(S)

Aim 1 analyses (Primary Aim) will compare and contrast the 4 pre-specified ATSSs embedded in the SMART design to determine whether one is clearly better or worse than the others with respect to mean suicidal ideation (SI) and suicide-related behaviors (NSSI and suicide attempts), which are the primary outcomes, at the end of 14 weeks of treatment. The data analysis method of Robins and colleagues^{160,161} will be used to contrast the 4 ATSSs based on reducing

suicide-related risk behaviors (SI, NSSI, and suicide attempts) to determine whether any of the interventions appear to be clearly better or worse than others. As part of the design, a student participant will contribute differentially to one or more of the 4 strategies (depending on the treatments to which he or she is randomized and whether he or she is a treatment responder), requiring a weighted comparison. Specifically, this analysis involves a weighted comparison of the cells A+B vs. A+C vs. D+E vs. D+F (see Table 8); the method by Robins and colleagues^{160,161} weights each student participant using the known randomization probabilities. Linear contrasts among the components of the ATSSs will be performed to further understand impact on efficacy. Similar analyses will compare the 4 strategies on the follow-up and secondary outcomes outlined above. Additionally, in response to reviewers' input, a composite outcome including suicidal ideation, suicide attempts, and NSSI will be derived. Death by suicide will be tallied but not included in the composite score. Song and colleagues¹⁶² provide a thorough discussion of the best ways to create composite scores, especially when dealing with a mixture of continuous and count outcomes. The analysis team will determine the best approach in the formation/derivation of the composite using the steps discussed by Song et al¹⁶². Similar analyses will compare the 4 strategies on the derived composite as outlined above.

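### The blinded evaluators who rate the SSI and SITBI also take a treatment history covering psychotherapy, query the counselor and may judge relatedness to the intervention, which creates avoidable chances of unblinding

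*Combined protocol and SAP*

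**What the plan says.** **Blinding.** Section 6.3 states: "All assessments of the main endpoints will be performed by the independent evaluators (IEs), who will remain blind to treatment status". The two primary measures, the SSI and the SITBI, are evaluator interviews (8.1). Section 9.3.1 adds that "suicidal ideation is the primary DV due to relatively low rates of suicidal behaviors post-baseline with college students", and 9.3.2 sets the Aim 1 comparison "at the end of 14 weeks of treatment".

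**Treatment history.** Section 6.5 refers to the "treatment history form that is completed by the student participant and the IE", and Table 1 lists the THI among the evaluators' measures. Section 8.1 defines it broadly, with psychotherapy and comprehensive treatment programs among the items, and schedules it at baseline, end of Stage 2 and follow-up.

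**Counselor contact.** After a missed assessment, 7.3 says: "The IE will ask the counselor if the student participant has changed phone number/email, is attending therapy". Counselors know the assignment, because under 6.1.4 the coordinator will "reveal randomization results to an already assigned counselor".

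**Relatedness.** Section 8.3.3.2 has the relationship of adverse events to study procedures, with the intervention expressly included, assessed by the "treating counselor and/or IE based on the temporal relationship" and clinical judgment.

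**Safeguards.** Section 6.3 has students and counselors reminded not to disclose treatment to evaluators. Evaluators also record a guess of the treatment group at the end of Stage 1 and, where applicable, Stage 2.

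**The concern.** None of the treatments can be masked from the student or the counselor, so the blind on the primary outcome rests on the evaluator alone. The SSI is an interviewer-rated scale from 0 to 38. A rater who believes a student is in CC-DBT or CAMS can score borderline items differently without intending to. Section 6.3 treats disclosure as something a student or counselor might volunteer. It does not deal with the protocol itself sending the evaluator to ask about treatment, to speak with an unblinded counselor, or to consider whether an event came from the intervention. What is at stake is the credibility of the blinded rating at week 14 and week 26.

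**Working it through.** The point is procedural, so the check sets the sections side by side.

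**1. Treatment history (main channel).**
- Timing: 8.1 and Table 1 put the THI at the end of Stage 2 and at follow-up. Section 4.2 puts those visits at weeks 14 and 26, and the SSI and SITBI are rated at both. Week 14 is the Aim 1 time point.
- Scope: 6.1.6 says the THI documents treatment received outside the study, and 9.3.7 says it captures services outside the universities. The definition in 8.1 carries no such limit and does not exclude study therapy.
- Order: no section places the SSI and SITBI before the THI. Table 1 lists the THI last among the evaluator measures, but does not present the list as a sequence.
- Carry-over: anything learned at week 14 is known at week 26 if the same evaluator sees the student, whatever the order within the week-14 visit.
- Cue: skills training belongs to CC-DBT (4.4, 6.1.5), so a student who describes it gives a strong hint. This is an inference. Section 8.1 does not name skills training as THI content.

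**2. Counselor query (lesser).** It arises only after a missed assessment. Attendance alone does not identify the arm, and since the same counselors deliver all treatments (9.3.7), the counselor's identity does not either. The query does require direct contact with an unblinded person, and it may show whether a student is in active treatment or maintenance.

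**3. Relatedness (lesser).** The evaluator's role is permitted, not required, and the rating discloses no assignment. It invites the evaluator to think about, or ask about, the treatment received.

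**4. Safeguards against these channels.** The counselor reminder bears directly on channel 2, and the student reminder partly on channel 1. Neither sets a script, an order or a limit on scope. The guess is collected at the ends of the stages and none is specified for week 26. No analysis of the guesses is specified.

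**5. Scale, for illustration only.** The documents give no figure for rating bias. Section 9.2 gives, for Aim 2, SD 7, 240 per arm, two-sided alpha 0.025 and 85% power at d = 0.30.
- Reproducing the plan's figure: 0.30 × √(240/2) = 3.286; the critical value is 2.241; Φ(3.286 − 2.241) = 85.2%, which agrees with 85%.
- Standard error of the difference: 7 × √(2/240) = 0.639 points.
- With no true effect and a net between-arm rating bias of b points, type I error = 1 − Φ(2.241 − b/0.639) + Φ(−2.241 − b/0.639).

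| Assumed b (SSI points) | b/0.639 | Type I error |
|---|---|---|
| 0.1 | 0.156 | 2.7% |
| 0.25 | 0.391 | 3.6% |
| 0.5 | 0.782 | 7.4% |
| 1.0 | 1.565 | 24.9% |

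Here b is an average over all participants, all in one direction. It is an assumption, and nothing in the documents shows which row, if any, applies. The table concerns the Aim 2 contrast, not Aim 1.

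**The case against.** The strongest reply is that none of these duties is designed to reveal the arm. The THI is described in two places as recording outside treatment, and study sessions are tracked through the electronic record (4.4, 6.4). The counselor query concerns contact details and attendance, and counselors are told not to disclose. Relatedness can be judged without knowing the assignment. The evaluator is also the natural observer of distress during assessments, which 8.3.1 lists as an adverse event. Evaluators are trained and certified, with continuing interrater checks (8.1, 10.1.8). Detailed ordering and scripts may sit in the procedure manuals, which are not part of these documents.

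Much of this stands. A reader might infer that all three tasks disclose treatment; the documents do not support that. The second and third do not reveal the arm by themselves, and the first does so only if study therapy comes up in the interview. The point about assessment distress is also sound, and rules out simply removing the evaluator from 8.3.3.2.

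What does not fall away is the THI. The broad definition in 8.1 and the narrower descriptions in 6.1.6 and 9.3.7 have not been reconciled. The interview falls at the primary time point, and no stated rule protects the ratings from it. Certification and interrater checks address scoring consistency; they do not keep an evaluator from learning the arm.

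**Conclusion.** The plan requires blind evaluators and then gives them duties that create avoidable opportunities for unblinding. The THI at weeks 14 and 26 is the main one; the counselor query and the relatedness option are lesser. The safeguards in 6.3 reduce or detect unblinding without closing these channels.

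The documents show a risk, not that unblinding happens. A reader might also infer a specific bias, for instance 0.5 to 1.0 SSI points, or 25% to 50% of the 2-point target in 9.2. There is no basis for that in the documents: the lesser channels touch only students who miss a visit or have an adverse event, and no rate or rating shift is given for any of the three. The conclusion rests on the text as written, and on the assumption that no unseen manual already fixes the order and scope of the THI. The change is worth making because it is cheap and protects an interviewer-rated primary outcome.

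**What to change.** 1. **Section 7.3:** have the project coordinator or the study liaison, not the evaluator, contact the counselor. The coordinator already handles assignments (6.1.4), and the liaison already links the counseling center and the study (4.1).
2. **Sections 6.5, 8.1 and Table 1:** have existing non-evaluator staff take the post-baseline THI. If the evaluator must take it, restrict it to non-study treatment, and at each visit complete and lock the SSI, the SITBI and the other evaluator ratings first. The first option is stronger, because locking protects only the ratings of that visit; the restriction to non-study treatment is then what protects week 26.
3. **Section 8.3.3.2:** limit the evaluator to relatedness to assessment procedures, and leave relatedness to the intervention to the counselor or the PI. This keeps the witness of assessment distress in the process.

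The cost is a small added burden on coordinators, and some THI training if the interview moves to other staff. No outcome, visit or sample size changes.

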8 STUDY ASSESSMENTS AND PROCEDURES

8.1 ENDPOINT AND OTHER NON-SAFETY ASSESSMENTS

We have divided measures into demographics, primary and secondary dependent variables (DVs), mediators, moderators, and implementation/process variables. Measures were selected if they: 1) fit the study aims, 2) have adequate psychometrics, 3) are listed as Common Data Elements in NIH or have been used in previous SR studies, 4) have shown sensitivity to change, 5) have been used with college students, 6) map onto the RDoC categories (Negative Valence Systems, Positive Valence Systems, Cognitive Systems, Social Processes, and Arousal and Regulatory Systems),⁷⁹ 7) are directly relevant to the application of CAMS or DBT, and 8) allow for reduced burden to student participants—the latter in response to reviewers' concerns.

Demographic Variables.

With student participants' consent, age, marital status, family income, residence, GPA, race, year in school, major, ethnicity, sexual orientation, cultural identity, and gender identity will be obtained via EMR/the registrar or by completing the Demographic Information Form at baseline.

SMART Primary Tailoring Variable: Sufficient vs. Insufficient Response to Stage 1 Treatments. Unique to SMARTs are tailoring variables or variables upon which subsequent randomizations are based.⁵⁹ For this trial, sufficient treatment response will be the primary tailoring variable and assessed by the Clinical Global Impressions (CGI),¹⁰³ adapted to SR. As noted in Preliminary

Studies, the CGI, adapted to SR, showed high inter-rater reliability and construct validity; this fits with other studies demonstrating that non-blinded trained counselors typically can offer CGI ratings commensurate to blinded IEs.¹¹¹

In SMARTs, a tailoring variable is a tool for clinical decision-making, in this case deciding on response to treatment, and therefore it will be based on clinical assessments by providers (and not the IE).⁵⁹ Beginning at session 4 and following each subsequent session, the counselor will complete the 7-point Likert-style CGI developed in the CAMPUS feasibility study to rate overall improvement in SR since baseline from (1) “*Very much improved*” to (7) “*Very much worse*.” Sufficient response will be defined as an Improvement score of ≤ 2 (“*Much improved*” or “*Very much improved*”).

A student participant in Stage 1 showing significant worsening may be re-randomized to Stage 2 conditions earlier. Similarly, students who begin the study with significant suicidality and show no improvement after 4 sessions may also be considered for early randomization to Stage 2.

Primary DV: Suicide-Related Behaviors – Relevant to Aims 1, 2, and 3.

Recognizing that measurement of suicide-related behaviors is fraught with challenges,¹¹² we are defining SR as “suicidal ideation, attitudes, behaviors and plans which take into account severity, intent, and ability to cope with ideation without engaging in suicidal behaviors, such as planning/rehearsal, NSSI, suicide attempts (SAs), and suicide.” Our primary assessment measures for SR are two interviews to measure suicidal ideation (SI; defined as self-reported thoughts of suicide-related behavior) and suicidal behaviors, including suicide attempts and non-suicidal self-injury (NSSI). Suicides will also be tallied.

- 1) The Scale for Suicide Ideation—Current (SSI)^{99,113} is a 19-question interview that assesses the student participant’s highest SI in the past 2 weeks, including attitudes, behaviors, and plans. Each item is rated as 0,1, or 2 with a total scale of 0-38. The IEs will be trained and certified on the SSI.
- 2) The Self-Injurious Thoughts and Behaviors Interview (SITBI)¹¹⁴ is a 3-15-minute interview containing modules that assess SI, suicide plans, suicide gestures, suicide attempts, and NSSI. The SITBI has been used with college students.^{115,116} The IEs will be trained and certified on the SITBI.

Secondary DVs/Covariates: Functioning – Relevant to All Aims

- 1) The CCAPS-34¹⁰⁷ assesses key domains of college student mental health (Depression, Generalized Anxiety, Social Anxiety, Academic Distress, Eating Concerns, Substance Use, and Hostility/Anger) and an overall Distress Index score. Students respond to questions using a 5-point rating scale (“*not at all like me*” to “*extremely like me*”). The CCAPS-34 takes only 2-3 minutes to complete¹⁰⁷ and is widely used in CCCs.²²¹ The CCAPS will be assessed at all assessment points and at every session. The question on SI will screen prospective participants and the weekly administration can track SI fluctuations more frequently.

- 2) The CGI-I and CGI-S¹⁰³ are secondary DVs when completed by IEs, counselors, and student participants—allowing for differences among reporters to be evaluated. The pilot data provided support for the inter-rater reliability and construct validity of this measure.
- 3) Academic Functioning will be obtained via self-report by student participants. Academic functioning will include cumulative grade point average, enrollment status, and number of credits attempted vs. completed.

Mechanisms of Change/Mediators of Treatment – Relevant to Aim 4

- 1) The measures listed below include those found in prior studies (some by our team) to mediate outcome in DBT (#1-3) and CAMS (#4-5). The Difficulties in Emotion Regulation Scale (DERS)¹¹⁷ includes 36 items rated on a 6-point scale to assess awareness and understanding of emotional experience, acceptance of emotions, ability to modulate emotional arousal, and effective action in the presence of intense emotions. See Preliminary Studies section.
- 2) The DBT-Ways of Coping Check List (DBT-WCCL)¹⁰⁴ is a 59-item self-report questionnaire measuring the use of DBT skills and dysfunctional, non-DBT coping strategies over the previous month. All items are rated from 0 to 3 (“never use” to “always use”). The DBT-WCCL includes two subscales, one assessing coping via DBT skills and one assessing coping via dysfunctional means. See Preliminary Studies section.
- 3) The Acceptance and Action Questionnaire II (AAQ-II)¹¹⁸ is a 7-item self-report measure of experiential avoidance rated on a 7-point scale (“never true” to “always true”). See Preliminary Studies.
- 4) The Suicide Cognitions Scale (SCS)¹¹⁹ is an 18-item self-report measure based on the residual risk model with Unlovability, Unbearability, and Unsolvability subscales. It predicted SI after controlling for depression severity and hopelessness¹²⁰ and uniquely discriminated SR between control and CAMS care.¹⁰⁶
- 5) The Optimism and Hope Scale (OHS)¹⁰² is a 14-item self-report measure used to assess a combination of dispositional optimism and trait hopefulness.
- 6) PROMIS Self-Efficacy for Managing Emotions-Short Form 4a is a 4-item self-report measure which asks participants to rate, at that moment using a 1 (I am not at all confident) to 5 (I am very confident) scale, the following four items: (1) I can bounce back from disappointment, (2) I can avoid feeling discouraged, (3) I can find ways to manage stress, (4) I can handle negative feelings.

Moderators of Treatment—Relevant to Aim 5

Aim 5 pertains to the identification of predictors and moderators of treatment response, which could be incorporated as secondary tailoring variables in later studies or during dissemination. Potential predictors and moderators were gleaned from the suicidology literature and/or from DBT and CAMS specifically:

- 1) History of previous suicide attempts has been predictive of SR and moderated treatment response.³¹
- 2) Personality Assessment Inventory – Borderline Features Scale (PAI-BOR)¹²³ is commonly used to assess BPD features in college students.^{124,125} The scale consists of 24 items, rated

on a 4-point scale, with a 0-72 range (38 is the cutoff for significant BPD features). BPD features has served as a proxy for chronicity.³²

- 3) Optimism and Hope Scale (OHS)¹⁰² See above. The OHS has been able to predict subsequent death by suicide.¹²⁶
- 4) Global Assessment Scale (GAS)¹²⁷ is a measure of an individual's social, psychological, and work- related functioning ranging from 1 to 100 (higher is better) and will be completed by the IE.
- 5) Sexual orientation, gender identity, and cultural identity will be assessed as sexual and gender minorities (SGM)/LGBTQ+ individuals are at an increased risk for suicide, suicide attempts, NSSI, and SI.^{18,19} Importantly, there are still large research gaps within this population (see¹²⁸). Given the growing number of college students who identify as non-binary or transgender or with another culture, our large multisite study will add to the literature regarding this population.¹²⁹
- 6) Alcohol Use Disorders Identification Test (AUDIT)¹⁸⁵ is a 10-item self-report measure of the severity of problematic alcohol use.
- 7) Drug Abuse Screening Test (DAST)¹⁸⁶ is a 10-item self-report measure of the severity of problematic substance use.

Implementation and Process Measures – Relevant to Aim 6

The implementation monitoring plan will be guided by 1) critical steps of the Quality Implementation Framework (QIF)³⁶; 2) process evaluation and implementation monitoring outlined by Saunders¹³⁵; and 3) implementation outcomes specified by Proctor.³⁵ The process evaluation will include both quantitative and qualitative assessments to monitor the implementation activities and address barriers that may arise during the study. The mixed methods will include feedback from the student participants, counseling staff, and directors.

- 1) Client Satisfaction Questionnaire (CSQ-8)¹³⁶ is an 8-item questionnaire that assesses clients' satisfaction with treatment and has been used in other CAMS studies.⁶⁶ See Preliminary Studies.
- 2) CSQ-8 (Therapist Version) and Reasons for Termination Checklist. Counselor participants' acceptability of and satisfaction with the interventions will be assessed at the end of Stage 1 and Stage 2 via the therapist version of the CSQ and Reasons for Termination Checklist. These measures were used in other CAMS⁶⁶ studies and our pilot.
- 3) Treatment Credibility Questionnaire. After session 1 of each stage, student participants will rate the therapy they are receiving on seven items adapted from Borkovec and Nau¹³⁷ that ask how logical, scientific, or potentially helpful the treatment appears to be.
- 4) Therapist Expectations. Two Likert-style questions regarding expectations about treatment utilized in prior studies⁶⁶ will be completed by counselor participants at the end of the first session in Stage 1 and Stage 2.
- 5) Treatment History Interview (THI)¹³⁸ is an interview to gather information about a client's psychiatric and medical treatment over a period of time, including psychotherapy, comprehensive treatment programs, case management, self-help groups, inpatient units, emergency treatment (e.g., emergency room visits, police wellness checks), medical treatment, as well as the use of psychotropic and other medications. The THI will be

collected at baseline, end of Stage 2, and follow-up. Data will be utilized descriptively and for cost analyses.

- 6) Telehealth Usability Questionnaire (TUQ)¹⁸⁷ is a 15-item questionnaire that assesses student participants' acceptability with using telehealth platforms for therapy.
- 7) TUQ-C (Counselor Version) is an adapted version of the TUQ questionnaire that assesses counselor participants' acceptability with using telehealth platforms for therapy. Counselors who provide DBT skills training via telehealth will also complete an adapted TUQ for DBT skills training.
- 8) Focused Interview. Counselor participants will each complete a focused interview at the end of their participation in the study. An independent party will conduct the focused interviews, which will center on each participant's experience of the study.
- 9) Counselor Session Telehealth Questionnaire (CSTQ). The CSTQ will be used to assess counselor perceptions of the technical adequacy of the virtual modality used during telehealth with their clients as part of the CAMPUS study. The CSTQ will also be used to evaluate counselor perceptions of comfort conducting therapy and risk assessment for heightened risk clients over a virtual format. The CSTQ is a 5-item measure and will be completed after every telehealth session.

Counselor Measures – Relevant to Aim 7

Aim 7 will explore aspects of counselor participants' experiences, including their beliefs about suicide, self-identified theoretical orientation and training experiences, expectations for and satisfaction with providing different types of therapy during the study, and general experiences of participating in the study.

- 1) CSQ-8 (Therapist Version) and Reasons for Termination Checklist. See above.
- 2) Therapist Expectations. See above.
- 3) Focused Interview. See above.
- 4) Zero Suicide Workforce Survey (Abbreviated). The Zero Suicide Workforce Survey (Abbreviated) assesses counselor participants' beliefs about suicide, techniques that counselor participants implement with suicidal clients, and confidence in their ability to treat suicidal clients.
- 5) Demographic Information Form. The Demographic Information Form will assess counselor participants' self-reported gender, race, ethnicity, sexual orientation, education level, years of clinical experience, years of experience working with suicidal clients, theoretical orientation, and experience with suicide, CAMS, and DBT.
- 6) TAU Questionnaire. The TAU Questionnaire will assess the interventions that counselor participants implemented during TAU. Counselor participants will complete this measure at the end of Stage 1 for each student participant they treat who was randomized to TAU.

